4.11.2 Clinical Laboratory Tests and Electrocardiogram

Clinical laboratory and ECG data will be presented for each treatment group using descriptive statistics based on the observed values and change from baseline values at each scheduled visit of the double-blind period, using the Double-Blind Safety Population. Summary statistics (n, mean, median, SD, minimum, and maximum) will be calculated for quantitative safety data and frequency counts will be compiled for classification of qualitative safety data. This will be repeated for visits corresponding to the open-label period, using the Open-Label Safety Population.

The number and percentage of patients with laboratory values that shift categories (i.e., below/within/above normal range) will be tabulated for each study visit and worst post-baseline visit during the double-blind period. This will be repeated using the Open-Label Safety Population as well as the Fosmetpantotenate Safety Population, for their respective treatment periods.

In addition, the number and percentage of patients with “potentially clinically significant laboratory values” (based on ranges defined below) will be summarized by treatment group, using the Double-Blind Safety Population and the Open-Label Safety Population.

Category	Parameter	Potentially Clinically significant ranges
Hematology	Hemoglobin	≤ 95 g/L (female), ≤ 115 g/L (male)
	Hematocrit	≤ 0.32 L/L(female); ≤ 0.37 L/L (male)
	Leukocytes	≤ 2.8 x 10 ⁹ /L
	Platelets	≤ 75 x 10 ⁹ /L; ≥ 700 x 10 ⁹ /L
Coagulation	PT-INR	≥ 2.0
	aPTT	≥ 43 seconds

Category	Parameter	Potentially Clinically significant ranges
Blood Chemistry	Calcium	< 1.75 mmol/L > 3.0 mmol/L
	Chloride	< 90 mmol/L > 115 mmol/L
	Creatinine	> 176.8 umol/L
	Glucose	< 2.8 mmol/L > 13.9 mmol/L
	Phosphate	< 0.6 mmol/L > 1.6 mmol/L
	Potassium	< 3.0 mmol/L > 5.5 mmol/L
	Sodium	< 130 mmol/L > 150 mmol/L
	Blood urea nitrogen	> 10.7 mmol/L
Liver Function Tests	Albumin	<25 g/L
	Total Protein	< 45 g/L
	ALT	> 3x-, 5x-, 10x-, and 20xULN
	AST	> 3x-, 5x-, 10x-, and 20xULN
	ALT and AST	Both ALT and AST > 3x-, 5x-, 10x-, and 20xULN
	Total Bilirubin	>ULN and >2xULN
	ALP	>2.5xULN
	ALT and Total Bilirubin	ALT >3xULN + total bilirubin > >2xULN, or international normalized ratio (INR) > 1.5
	AST and Total Bilirubin	AST >3xULN + total bilirubin > >2xULN, or international normalized ratio (INR) > 1.5

For ECG measurements, QTc intervals will be determined using the Fridericia correction (QTcF) and the Bazett correction (QTcB). The QTcF and QTcB values and their change from baseline at each scheduled visit of the double-blind period will be summarized using descriptive statistics. The number and percentage of patient with elevated values (per ICH E14 criteria) will also be tabulated. This will be repeated using the Open-Label Safety Population, for visits in the open-label period.

All clinical laboratory safety data, including measurements obtained from the 12-lead electrocardiogram (ECG), will be listed for individual patients across all visits in the double-blind and open-label periods. Values identified as potentially clinically significant (laboratory values) or elevated (ECG values) will be flagged.

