10.3. Adverse Events of Interest (AEOI)

Abnormalities in ALT, AST and total bilirubin are considered AEOIs and must be reported to the Sponsor's Medical Monitor within 24 hours of awareness if one of the following conditions are met:

- The abnormality represents a new elevation in ALT or AST >3 times the upper limit of normal (ULN), with or without an elevation of total serum bilirubin >2 times ULN; or
- The abnormality represents a 2-fold increase in ALT or AST above the baseline value in patients who had elevated values prior to starting study medication.

In such instances, the following steps will be taken:

1. Temporarily discontinue study medication.
2. Repeat testing of ALT, AST, alkaline phosphatase and total bilirubin, to be completed within 48 to 72 hours (if possible) to confirm the abnormalities.
3. If the abnormality is confirmed by repeat results or after consulting with Sponsor Medical Monitor:
 - a. Complete an AEOI Report Form that documents both the liver function test findings and any associated signs or symptoms, and report by email to the SAE contact on the [Study Contact Information](#) page of this protocol.
 - b. Monitor liver enzymes and serum bilirubin 2 or 3 times weekly. The frequency of re-testing can decrease to once weekly or less if the abnormalities stabilize and the patient is asymptomatic.
 - c. Perform additional testing to evaluate liver function, as appropriate (eg, international normalized ratio [INR], direct bilirubin).
4. Do not resume study medication until monitoring indicates abnormalities have resolved or stabilized.

Patients would not typically be allowed to resume study medication if they have:

- ALT or AST >8 times ULN
- ALT or AST >5 times ULN for more than 2 weeks
- ALT or AST >3 times ULN and total bilirubin >2 times ULN or INR >1.5
- ALT or AST >3 times ULN with symptoms of fatigue, nausea, vomiting, right upper quadrant pain or tenderness, fever, rash and/or eosinophilia (>5% eosinophils)

Management of such patients should be closely coordinated with the Sponsor's Medical Monitor. In addition to monitoring liver function tests, the Investigator should perform other relevant clinical and laboratory measurements to identify potential causes of the abnormalities (eg, acute viral hepatitis types A, B, C, D, and E; autoimmune or alcoholic hepatitis; non-alcoholic steatohepatitis; biliary tract disease or exposure to hepatotoxic medications or environmental chemical agents).

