Cases of increased liver function tests will always be considered serious (ie, medically important) if they meet both the following criteria:

- Study medication is suspected to have caused hepatocellular injury, generally shown by a confirmed elevation of 3-fold or greater above ULN in ALT or AST; and,
- The ALT or AST elevations are accompanied by a total bilirubin >2 times the ULN or INR >1.5, without initial findings of cholestasis (elevated serum alkaline phosphatase)

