4.2 Determination of Sample Size

It is estimated that a total of 74 patients (37 in each treatment group) will provide approximately 80% power to detect a 3-point difference between groups in the average change from baseline score for the PKAN-ADL, based on Student's t-test with alpha=0.05 (two-sided); this calculation assumes a standard deviation of 4.5 points for the change from baseline scores. Allowing for 10% attrition, a total of 82 patients will be randomized to achieve the target sample size of at least 74 patients completing the double-blind period of the study.

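### SAP 4.11.2 punctuates its two combined liver rows so that, if coded literally, an INR above 1.5 counts even when ALT and AST are normal

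*SAP*

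**What the plan says.** SAP section 4.11.2 lists ranges for potentially clinically significant laboratory values. Patients meeting them are counted, "based on ranges defined below) will be summarized by treatment group, using the Double-Blind Safety Population and the Open-Label Safety Population". Values so identified are also flagged in the by-patient listings.

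Under Liver Function Tests, two rows combine analytes, and each is labelled with one transaminase together with bilirubin. The range given in the ALT row is "ALT >3xULN + total bilirubin > >2xULN, or international normalized ratio (INR) > 1.5". Its counterpart for the other enzyme has the same form and the same comma: "AST >3xULN + total bilirubin > >2xULN, or international normalized ratio (INR) > 1.5".

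The Coagulation part of the same table has a separate PT-INR row with a threshold of 2.0 or more.

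Protocol section 10.3 uses similar thresholds to say when a case of raised liver tests is always serious. Both of its criteria must be met. The first is suspected drug-induced hepatocellular injury, "generally shown by a confirmed elevation of 3-fold or greater above ULN in ALT or AST; and". The second is: "The ALT or AST elevations are accompanied by a total bilirubin >2 times the ULN or INR >1.5". That second criterion also rules out cases that start with cholestasis.

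**The concern.** In the SAP rows the plus sign ties the transaminase to bilirubin, and the comma then sets INR off as an alternative to that pair. Nothing in the SAP links the INR limb to a raised transaminase. A programmer who follows the cell as written would therefore count patients with no transaminase elevation in rows labelled as transaminase plus bilirubin.

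The liver deserves a clean count in this trial. Abnormal ALT, AST and bilirubin are the only adverse events of interest that the protocol defines (section 10.3). The rat studies showed hepatocellular necrosis with raised ALT (section 4.1.1), and one compassionate-use patient had reversible transaminase elevations (section 4.1.2). With about 41 patients per arm, a single misclassified patient is visible in a table of this kind.

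**Working it through.** The point concerns a logical definition, so the plan has no figure to reproduce. The check compares the two rules over every combination of findings and then illustrates the scale.

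**Definitions**

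- A = ALT >3xULN (or AST >3xULN, for the AST row)
- B = total bilirubin >2xULN
- I = INR >1.5
- SAP as punctuated: (A and B) or I
- Nesting in protocol 10.3, seriousness criteria: A and (B or I)

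**All eight combinations**

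| A | B | I | SAP as punctuated | Protocol nesting |
|---|---|---|---|---|
| 0 | 0 | 0 | no | no |
| 0 | 0 | 1 | **yes** | **no** |
| 0 | 1 | 0 | no | no |
| 0 | 1 | 1 | **yes** | **no** |
| 1 | 0 | 0 | no | no |
| 1 | 0 | 1 | yes | yes |
| 1 | 1 | 0 | yes | yes |
| 1 | 1 | 1 | yes | yes |

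The rules differ in 2 of 8 patterns. Both have INR above 1.5 without the transaminase elevation. The punctuated rule never misses a case that the nested rule would count; it only adds cases.

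**Consistency within the SAP table.** Take normal ALT, AST and bilirubin with an INR of 1.6. The patient does not meet the table's PT-INR range (2.0 or more) but would be counted in both combined liver rows. With an isolated INR of 2.0 or more, the patient would be counted in three rows: PT-INR, ALT combined and AST combined.

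**Size of one case.** SAP section 4.2 states that "a total of 82 patients will be randomized to achieve the target sample size of at least 74 patients completing the double-blind period". Randomization is 1:1, so an arm has about 82/2 = 41 patients. One spurious case is 1/41 = 2.4% of an arm, in each of the two rows.

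**How often it might happen.** The documents give no rate of isolated INR above 1.5, so the share p below is an assumption.

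- Expected spurious cases per arm = 41p
- Chance of at least one among all 82 patients = 1 − (1 − p)^82

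| Assumed p | Expected per arm | Chance of at least one in 82 |
|---|---|---|
| 1% | 0.41 | 56.1% |
| 2% | 0.82 | 80.9% |
| 5% | 2.05 | 98.5% |

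**Opportunity.** The protocol's double-blind schedule (section 15.1) has coagulation at Screening, Week 12, Week 24 and the End of Treatment/Early Termination visit. Screening precedes dosing, so a patient who completes the period on treatment has two scheduled on-treatment INR readings. Coagulation testing continues in the open-label period, where the same table is produced.

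**The case against.** The strongest reply is that the intent is easy to recover. The rows sit under Liver Function Tests and are labelled as transaminase and bilirubin. A separate INR row at 2.0 shows that an isolated 1.6 was not meant to be flagged, and the protocol's seriousness criteria give the proper nesting. A careful programmer may well code it correctly. This stands, and it is why the miscount is conditional on literal coding. It does not remove the defect: the SAP states a counting rule, and that rule followed as written gives the wrong count.

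A second reply is that the protocol is also loose. Its list of circumstances in which study medication would not typically be resumed has "ALT or AST >3 times ULN and total bilirubin >2 times ULN or INR >1.5", again without brackets. That is fair, so the comparison here rests only on the seriousness criteria in the same section, where INR plainly has to accompany the transaminase elevation.

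A third reply is that the cell contains a doubled greater-than sign, so its punctuation may not be reliable. The sign may be a typing slip or an artefact of text extraction. Nothing here depends on it, and the ALT and AST rows carry the same comma.

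A reader might infer that these rows are the trial's main liver signal and that false cases could create or hide one. The documents do not support that:

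- The SAP calls the ranges only potentially clinically significant.
- It also reports ALT, AST, both together, and bilirubin in separate rows. It adds shift tables, incidence and time-to-first-event analyses of adverse events of interest, and by-patient listings.
- A correct combined count cannot exceed the matching >3xULN count, so a combined row larger than that row would expose the error. The check is only partial: with three patients above 3xULN and one spurious case in the combined row, nothing looks wrong until the listings are read.

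**Conclusion.** The concern holds in a limited form. As punctuated, both combined rows admit INR above 1.5 without a transaminase elevation. This conflicts with the nesting in protocol 10.3 and sits badly with the table's own INR threshold of 2.0.

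The effect is confined to descriptive safety tables and listing flags; no efficacy result, test or error rate changes. One affected patient adds about 2.4% to an arm in each row. The frequency is unknown: the 1% to 5% range above is assumed, and it matters only if the rows are coded literally. That true combined cases will be few, so that one false case would stand out, is likewise an assumption and not a figure from the documents.

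The wording does not show that patients with normal ALT and AST will in fact be counted, nor that liver injury would be misjudged overall. It shows that the written rule allows the first, and that other outputs would help to reveal it. This is a minor correction, worth making because it is nearly free.

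**What to change.** Rewrite the two rows in SAP section 4.11.2 with explicit brackets:

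- ALT >3xULN AND (total bilirubin >2xULN OR INR >1.5)
- AST >3xULN AND (total bilirubin >2xULN OR INR >1.5)

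This follows only the and/or nesting of the seriousness criteria in protocol 10.3. It does not reproduce their requirements for a confirmed elevation, suspected drug causation and absence of initial cholestasis, so the rows should not be described as the protocol's definition of a serious liver case.

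Also state whether the values must come from the same visit. The choice matters because coagulation is scheduled at fewer double-blind visits than chemistry: a same-visit rule would leave the INR limb assessable only where both were drawn.

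The cost is brackets in two table rows, one sentence on timing and one derivation in the programs. Data collection, patients and power are unaffected.

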4.11.3 Physical Examination and Vital Signs

Reported abnormalities during the double-blind period and open label period, will be tabulated by body system for patients in the Double-Blind and Open-Label Safety Populations, respectively. Changes in physical examinations will be described in the text of the final study report. A by-patient listing will be provided, which presents physical examination results across all assessments in the double-blind and open-label periods.

Vital signs (systolic and diastolic blood pressure, heart rate, respiration rate, and temperature), and body weight will be summarized by treatment group using descriptive statistics. Summary statistics (n, mean, median, SD, minimum, and maximum) will be calculated for both the actual value and the change from baseline value at each scheduled visit during the double-blind period. This will be repeated using the Open-Label safety population for visits during the open-label period.

For systolic and diastolic blood pressure, as well as weight, figures will be presented which show observed values, as well as change from baseline, by treatment group, for each visit during the double-blind period and open-label period, for patients in the Double-Blind and Open-Label Safety Populations, respectively.

In addition, the number and percentage of patients who meet the following criteria at any time during the double-blind period and open-label period will be summarized for each of the respective safety populations:

- Severe blood pressure elevation
 - Systolic blood pressure \geq 180 mm Hg; **OR**, diastolic blood pressure \geq 120 mm Hg
- Moderate blood pressure elevation
 - Systolic blood pressure \geq 140 mm Hg **OR**, diastolic blood pressure \geq 90 mm Hg

Patients with potentially clinically significant changes from baseline (i.e., elevated values per criteria above) will be summarized and flagged in data listings.

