2.4 Safety Endpoints

The safety and tolerability of fosmetpantotenate will be assessed based on the occurrence of adverse events (AEs) and by serial vital signs including weight, physical examinations, clinical laboratory parameters (chemistry, hematology, coagulation, and urinalysis), the Columbia Suicide Severity Rating Scale (C-SSRS) (in assessable patients), and 12-lead electrocardiograms (ECG).

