4.6 Demographics and Baseline Characteristics

Demographic data (including age, race, ethnicity, sex, height, weight, Body Mass Index (BMI), and Body Surface Area (BSA), pre-treatment clinical characteristics, and baseline disease assessment scores will be summarized by treatment group for the Double-Blind FAS as well as the Double-Blind Safety Population. Descriptive statistics (n, mean, SD, median, minimum, and maximum) will be presented for continuous variables. Frequency distributions (counts and percentages) will be presented for categorical variables. This table will be repeated, stratified by age group (pediatric, adult).

Similar tables summarizing demographic and baseline data will be prepared for patients in the PPS, OL-FAS as well as the Open-Label Safety Population, grouped by prior double-blind treatment assignment and overall. In the event that the FAS and Safety Population are identical for either the double-blind or open-label periods, then the tables will only be produced for the Safety Population.

A by-patient listing will be provided, presenting data collected for demographics and baseline characteristics at Screening, for patients in the Double-Blind Safety Population.

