4.11.1 Adverse Events (AEs)

All AEs will be coded by Preferred Term and System Organ Class using MedDRA coding dictionary Version 20.0.

TEAEs in the double-blind period are defined as AEs that are new or are a worsening of an existing condition that begin from the day of first dose of investigational product until the day after the last dose for the double-blind treatment period. TEAEs in the open-label period are defined as AEs that are new or are a worsening of an existing condition that begin from the day of first dose of open-label investigational product. TEAEs in the fosmetpantotenate safety population are defined as AEs that are new or are a worsening of an existing condition that begin from the day of first dose of (blinded or open-label) fosmetpantotenate.

An overview of adverse events will be provided for each of the three Safety Populations that summarizes incidence in the following categories, overall, by age group (pediatric, adult), and by sex:

- Any AEs
- Any TEAEs
- TEAEs by relationship to study medication (Not related, Unlikely Related, Possibly Related or Related)
- TEAEs by severity (mild, moderate, severe)

- Any TEAEs with an outcome of death
- TESAEs
- Treatment discontinuation due to TEAEs

The incidence of TEAEs will be summarized for each treatment group by Preferred Term as well as by Preferred Term within System Organ Class. The incidence of TEAEs by severity and relationship to treatment will be summarized for each treatment group by System Organ Class and Preferred Term. A patient with several occurrences of the same AE will be counted once and classified by the most severe event (or the event with the closest relationship to study drug). If severity or causality is missing, the worst case will be assumed (i.e., “Severe” if severity is missing and “Drug Related” if causality is missing.)

In addition, the incidence of Adverse Events of Interest (AEOIs), TESAEs, TEAEs leading to treatment discontinuation, and TEAEs leading to death will be summarized for each treatment group by System Organ Class and Preferred Term.

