4.11.4 C-SSRS Scale

Columbia Suicide Severity Rating Scale is a suicide assessment questionnaire, which evaluates suicidal ideation and behavior. The questions after the screening visit are all based on “since last visit”.

Descriptive statistics will include the following tabulations by treatment group, with data pooled for pediatric and adult populations, across all visits of the double-blind period:

- The number (%) of patients with suicidal ideation or suicidal behavior at each visit: A “yes” answer at any time during treatment period to any one of the suicidal ideation and behavior questions.
- Shift tables that display the frequency of change in C-SSRS categories during the treatment period relative to baseline at each visit, as well as worst post-baseline visit.
- Severity, frequency, duration, controllability, deterrents, reason (for pediatric patients, only severity and frequency are collected) of suicidal ideation at each visit
- Actual and Potential Lethality/Medical Damage of Attempted Suicide (for actual attempts only) at each visit

The above tables will also be produced for visits in the open-label period, using the Open-Label Safety Population.

Data listings will provide individual patients’ responses to the C-SSRS questionnaire at all visits for each patient evaluated on this scale.

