4.12.1 Open-Label Efficacy Analysis

For the Interim Analysis, the scope of analysis of open-label efficacy data is limited to double-blind data. Open-label efficacy data will be included in the listings only.

A later version of the SAP will be released, which will describe the scope of open-label efficacy analysis for the Final Analysis. The analysis is outlined below:

The effects of fosmetpantotenate during the open-label use will be examined based on data from the OL-FAS.

For each efficacy endpoint collected in the open-label extension phase, scores will be tabulated using descriptive summary statistics (i.e., mean, SD, median minimum, and maximum for score totals; frequency tables for ordered categorical ratings) and graphical plots of mean values and mean change from baseline values at each study visit, overall

and by prior treatment in the double-blind period. For this purpose, baseline is defined as the last assessment prior to the first dose of open-label fosmetpantotenate.

On an exploratory basis, hypothesis testing will be applied to the primary and secondary efficacy endpoints measured during the open-label period to assess changes from Baseline, both overall and in the groups to which patients were initially randomized for the double-blind period (i.e., fosmetpantotenate or placebo). Between-group t tests will be used to explore whether improvement is greater for patients who convert to RE 024 from placebo, compared to those maintained on active investigational product for the open-label period. If the number of patients permits, mixed-effect linear models (as described for the primary efficacy analysis) may also be used to explore differences in the pattern of change over time between groups.

An additional exploratory analysis of PKAN-ADL may be undertaken using a mixed model, with Weeks since start of open-label treatment (continuous variable) as the fixed effect, baseline value (for the open-label extension period) as a covariate, and patient as the random effect. The first-order autoregressive AR(1) option will be used for modeling the covariance structure within-patient. The estimate of the time effect (i.e., rate of change) and its 95% CI will be obtained.

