4.12.2 Open-Label Safety Analysis

For the Interim Analysis as well as the Final Analysis, all safety data collected for the Safety Population during the open-label period of the study will be presented using descriptive statistics, including summary tables of AEs, summary tables and graphical plots of mean values over time for continuous measurements (e.g., vital signs, weight), and frequency tables for categorical data obtained at each study visit. Statistical methods and counting rules similar to those described for the double-blind treatment period will be applied. The last measurement obtained prior to the first dose of open-label fosmetpantotenate will serve as the baseline value for assessing change from baseline in clinical laboratory data and vital signs during the open-label period of the study.

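### Open-label weight is planned as raw kg with no stated age split, and serial pediatric height has no named analysis, so the safety summaries would not show whether children grow as expected

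*SAP*

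**What the plan says.** Weight belongs to a named safety endpoint: SAP 2.4 lists "serial vital signs including weight, physical examinations, clinical laboratory parameters". SAP 4.11.3 states that vital signs "and body weight will be summarized by treatment group using descriptive" statistics, for the value and its change from baseline at each visit, with figures by treatment group, and repeats the tables for the open-label population. Protocol 9.3.1 records weight in kilograms. The flagging rule in SAP 4.11.3 covers "Patients with potentially clinically significant changes from baseline (i.e., elevated values per criteria above"), and the only criteria above it are blood pressure elevations.

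SAP 4.11 lays out open-label safety for the whole cohort and, when indicated, by earlier double-blind treatment. Age group is not mentioned there. Elsewhere the SAP does write an age split: for the baseline table ("This table will be repeated, stratified by age group (pediatric, adult"), for the adverse event overview ("incidence in the following categories, overall, by age group (pediatric, adult), and by sex") and for the descriptive efficacy tables (SAP 4.10.1 to 4.10.3). For the C-SSRS it states the opposite, "with data pooled for pediatric and adult populations".

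Protocol 9.3.1 and Table 15.1-2 schedule serial height for patients under 18 at enrolment. The SAP names height only among baseline characteristics (4.6) and in the conversion, BMI and BSA formulas (6.2.3).

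SAP 4.12.2 applies the open-label safety summaries to both reports: "For the Interim Analysis as well as the Final Analysis, all safety data collected". SAP 4.12.1 promises more only for efficacy: "A later version of the SAP will be released, which will describe the scope of open-label efficacy analysis".

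**The concern.** Patients enter from age 6 and may stay on open-label drug for 278 weeks, about 5.3 years. SAP 4.12 makes long-term safety the main objective of that period. Everyone is then assigned active drug, so no concurrent control arm shows what weight or height would otherwise have done. For a growing child, the natural yardstick is an age- and sex-based reference, and the plan uses none.

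Without one, a positive mean change in kg or cm is uninformative: it appears under normal growth and under slowed growth alike. Combining children with adults up to age 65 dilutes it further. The reason to look is the disease itself. Protocol section 4 names malnutrition among the typical causes of early death and describes dysphagia leading to feeding tubes, and Protocol 6.5.1 expects underweight adolescents. At stake is how readable one long-term safety measure is in children. No test, endpoint or efficacy conclusion is involved.

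**Working it through.** The plan gives no figure to reproduce here. The check is a count from the schedule, followed by an illustration on stated assumptions.

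**Counts (Protocol Table 15.1-2).**
- Open-label weight visits: Weeks 30, 36, 48, 72, 96 and 120, plus seven from Week 146 to Week 302 = 13.
- Open-label height visits: Weeks 30, 72 and 120, plus the same seven = 10. Weight is also taken at all 10.

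**Assumptions (not in the documents).**
- Normal gain of 2 to 4 kg a year while growing; impaired growth is half of that.
- Pediatric share of 20% to 50%.
- Adult mean change of 0 kg, then 0.5 kg.
- Between-child SD of weight at a given age of 5 to 10 kg.
- SD of z-score change of 0.3 to 0.5.

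**Gain per child, Week 24 to Week 72.** 48/52.18 = 0.92 years.
- Normal: 0.92 × 2 to 4 = 1.84 to 3.68 kg.
- Halved: 0.92 to 1.84 kg.

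**Mean over all ages** = share × child gain + (1 − share) × adult change. The normal and halved columns take the adult change as 0. The gap is share × (normal − halved gain). The last column is 0.5 × (1 − share).

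| Pediatric share | Normal (kg) | Halved (kg) | Gap (kg) | Effect of 0.5 kg adult change (kg) |
|---|---|---|---|---|
| 20% | 0.37 to 0.74 | 0.18 to 0.37 | 0.18 to 0.37 | 0.40 |
| 35% | 0.64 to 1.29 | 0.32 to 0.64 | 0.32 to 0.64 | 0.33 |
| 50% | 0.92 to 1.84 | 0.46 to 0.92 | 0.46 to 0.92 | 0.25 |

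Every mean is positive. The adult change exceeds the whole gap at a 20% share, lies at the lower end of it at 35%, and is smaller than it at 50%.

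**Age split alone.** In a children-only kg table, normal growth at 2 kg a year and halved growth at 4 kg a year both give 1.84 kg. This pairs opposite ends of the assumed range, but it shows why a raw kg change needs a reference.

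**The same deficit as a weight-for-age z-score** = shortfall / SD, with the SD held constant.
- Week 72: −0.92/10 to −1.84/5 = −0.09 to −0.37.
- Week 120 (96/52.18 = 1.84 years, shortfall 1.84 to 3.68 kg): −1.84/10 to −3.68/5 = −0.18 to −0.74.
- Expected growth: 0.

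**Precision of a mean z change** = t × SD/√n, with no dropout.
- All children, 82 × 0.20 to 0.50 = 16 to 41: n = 41 with SD 0.3 gives 0.09; n = 16 with SD 0.5 gives 0.27.
- Per prior arm, about 8 to 20: n = 20 with SD 0.3 gives 0.14; n = 8 with SD 0.5 gives 0.42.

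**The case against.** The strongest reply is that no commitment is broken. Growth is neither an objective nor an endpoint, and weight, which is part of one, gets full descriptive statistics in both periods. That stands, and it makes this an improvement to the plan and not the repair of an error.

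The missing age split is partly read from silence. SAP 6.2 refers some table-specific rules to mock-ups that are not in the documents. A reader might infer that the SAP rules out an age split for weight, or that serial height will go unreported. Neither is supported. The general clauses in SAP 4.1 and 4.12.2 could produce a height table, and the by-patient physical examination listing could carry height, which Protocol 9.3.1 describes under that heading. These routes would still give only raw cm.

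The SAP introduction says that the document mainly serves the interim report, and a later version is coming, so growth tables could be added then. The data are collected regardless and nothing is lost. But SAP 4.12.2 already covers the final analysis, and the later version is promised only for efficacy.

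Other safeguards remain: adverse event reporting, safety review by the monitoring committee, weight-based pediatric dose checks every 24 weeks, and the minimum of the weight change, which would show an individual's loss.

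A reader might also infer that the drug is suspected of stunting growth. The documents do not support that. In Protocol 4.1.1, reduced weight gain was seen in male rats at 2000 mg/kg/day over 28 days, and it is not listed among the adverse effects in the 90-day rat study at doses up to 1250 mg/kg/day. Finally, PKAN itself may move children away from a healthy reference, so z-scores would describe growth without attributing it.

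**Conclusion.** The point holds as a worthwhile, inexpensive improvement. Followed as written, SAP 4.11.3 and 4.12.2 yield raw means in an uncontrolled period, and these cannot show whether children grow as expected. That conclusion rests on the text and on the fact that slowly growing children still gain kg and cm.

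The size rests wholly on assumed growth rates, pediatric share and SDs. It would be tempting to say that adult weight change swamps any growth deficit. That is clear only at a 20% pediatric share; at 50% the adult effect is 0.25 kg against a gap of 0.46 to 0.92 kg. Nor would z-scores settle the matter by Week 72: the assumed effect of 0.09 to 0.37 is close to the half-width for all children (0.09 to 0.27) and to that per arm (0.14 to 0.42). The double-blind weight comparison keeps its concurrent control and is not in question.

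**What to change.** In SAP 4.11.3 and 4.12.2:

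- Present weight by age group (pediatric, adult).
- For patients under 18 at enrolment, while they are within the reference's age range, add weight-for-age z-scores and, where height is measured, height-for-age and BMI-for-age z-scores. Show the observed value and the change by visit.
- Name the growth reference. The CDC 2000 charts, which the protocol cites for its 40 kg dose threshold, are one choice.
- Make all children combined the main display, with prior randomised arm as supportive only.

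The cost is SAP wording and a few descriptive tables from age, sex, weight and height already collected. No visit, sample size or alpha changes. The tables would be descriptive, imprecise with few children, and unable to separate drug from disease. Height may be hard to measure in dystonic or non-ambulant patients, and a US reference may fit other regions less well.
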